CMR	Cardiovascular magnetic resonance
ECG	Electrocardiogram
IMR	Index of microvascular resistance
HTPR	High on-treatment platelet reactivity
MVO	Microvascular obstruction
PW	Pressure Wire
PPCI	Primary percutaneous coronary intervention
SAE	Serious adverse event
STEMI	ST-segment elevation myocardial infarction
TIMI	Thrombolysis in myocardial infarction
UA	Unstable angina
VASP	Vasodilator stimulated phosphoprotein phosphorylation

KEYWORDS

Pharmacodynamic Antiplatelet Myocardial Infarction Cangrelor Ticagrelor STEMI IMR CMR

1. LAY SUMMARY

Major heart attacks are caused by a number of factors, the two major of which are furring up of a coronary artery with atheroma and then sudden clot formation on this area leading to a blockage and interruption of blood flow. The clots that lead to heart attacks are largely made of clotting blood cells (platelets) that in health repair blood vessels and inhibit spontaneous bleeding. One of the main treatment strategies for heart attacks is to make these cells less "sticky". Aspirin is a main stay of anti-platelet treatment in the UK and in addition one of three other oral antiplatelet agents acting on the same platelet activation pathway (P2Y₁₂ receptor) is licensed for use. When a patient is admitted with a major heart attack, they are treated with emergency primary percutaneous coronary intervention (PPCI) a technique where a wire and balloon are used to reopen the coronary artery and then usually a stent (a slotted metal tube) is placed to keep the artery open. Aspirin and one of the P2Y₁₂ inhibitor agents are given to prevent further clots and all have been shown to reduce negative events following heart attacks and angioplasty with stent insertion. There are increasing data, including from our own institution, showing that in the setting of heart attacks, the oral P2Y12 inhibitors are poorly absorbed and have little effect at the time of most need, i.e. soon after dosing while the primary PCI is being performed.

All three current $P2Y_{12}$ inhibitor agents are taken in tablet form immediately before the emergency PPCI procedure. It appears that in healthy stable patients these agents take at least 30 min to 2 hours to have an adequate effect. In heart attack patients the angioplasty procedure is usually performed well within this timescale. Furthermore, patients who are having a heart attack do not have normal drug absorption with blood being diverted away from the stomach and gut activity being suppressed by other drugs such as morphine.

In this current study, patients with major heart attacks will be given our standard oral agent, Ticagrelor, or the newer intravenous agent Cangrelor prior to PPCI. Blood samples will be taken to assess the effect of the anti-platelet agents when the balloon opens the artery and 4 hours after taking the drugs. A final sample will be taken at 24-36 hours to assess effect of the anti-platelet agents and also to assess myocardial damage.

We will assess the two drug therapies by looking at

- i) The effect of the drugs on blood platelet "stickiness"
- ii) The effect on patency of the treated artery (TIMI Flow Grade)
- iii) The effect on the ECG markers of success
- iv) The effect on the extent of heart muscle damage using Cardiac MRI scanning
- v) The effect on the flow in the capillary blood vessels in the heart muscle (Index of Microcirculatory Resistance, IMR) using an intracoronary pressure wire.

In total the patients in the study will require up to 3 extra blood tests, each using around 10-15 ml of blood (approximately 3 teaspoons of blood). This will not cause any ill effects but may involve up to 2 extra needle pricks (as the first sample will be taken from the radial or femoral sheaths and does not involve a needle prick). The angioplasty procedure itself will be prolonged slightly (after the "life-saving" part of the procedure when flow in the artery has been restored) by the introduction of a further coronary wire (pressure wire) to measure coronary pressure flow and the index of microcirculatory resistance (IMR).

Three months after the index admission, patients will undergo a Cardiac Magnetic Resonance Scan to assess the amount of heart muscle damaged.

2. INTRODUCTION

2.1 BACKGROUND

The success of modern treatment for ST-segment elevation myocardial infarction (STEMI) is dependent, in part, on the adequate suppression of platelet activity. Primary percutaneous coronary intervention (PPCI) for STEMI management has led to marked reductions in morbidity and mortality (1, 2). Aspirin is the mainstay anti-platelet agent. It is rapidly absorbed in the upper gastrointestinal (GI) tract and results in a measurable inhibition of platelet function within 60 minutes (3, 4). The advent of the platelet P2Y₁₂ inhibitors has led to further improvement in outcomes in patients with acute coronary syndromes (ACS) undergoing PCI with reduced ischaemic complications (5) albeit at an increase in rate of bleeding complications. These agents have a synergistic effect on platelet function with the addition of Clopidogrel to Aspirin leading to approximately 20% reduction in negative cardiovascular events (6).

Activation of platelets leads to a conformational change in the surface glycoprotein IIb/IIIa receptor that allows cross bridging with fibrinogen and rapid aggregation (platelet thrombus formation) (7, 8)

During PPCI, thrombus formation and dispersion can have a major impact on outcome. Intravenous platelet IIb/IIIa receptor antagonists such as Abciximab were initially shown to have a positive impact on primary angioplasty outcomes leading to a class IIa indication within the European Society of Cardiology (ESC) guidelines for use in the treatment of STEMI with angioplasty (9).

As oral antiplatelet inhibition has improved (specifically with the addition of Clopidogrel, Prasugrel or Ticagrelor) there has been a concomitant reduction in the use of intravenous IIb/IIIa agents during PCI for patients with ACS. This has been partly informed by later studies suggesting that the additive value of these agents to dual anti-platelet therapy is questionable (10).

In addition, the extra bleeding complications are seen by some to be excessive (11).

Current NICE recommendations for the treatment of STEMI include Aspirin plus one of the P2Y12 agents Clopidogrel, Prasugrel or Ticagrelor.

Ticagrelor, a reversible p2Y12 agent (cyclopentyltriazolopyrimidine CPTP) has been shown to be superior to Clopidogrel in ACS patients in the PLATO trial (12).

In this multicenter, randomized, double-blind trial, 18,624 patients were recruited. 7544 patients with STEMI were allocated to either Ticagrelor 180mg loading dose followed by 90 mg twice daily or Clopidogrel 300mg loading dose followed by 75 mg daily for 6 to 12 months. At 12 months, the primary end point — a composite of death from vascular causes, myocardial infarction, or stroke — had occurred in 9.8% of patients receiving Ticagrelor as compared with 11.7% of those receiving Clopidogrel (hazard ratio, 0.84; 95% confidence interval [CI], 0.77 to 0.92; P<0.001). Predefined hierarchical testing of secondary end points showed significant differences in the rates of other composite end points, as well as myocardial infarction alone (5.8% in the Ticagrelor group vs. 6.9% in the Clopidogrel group, P=0.005) and death from vascular causes (4.0% vs. 5.1%, P=0.001) but not stroke alone (1.5% vs. 1.3%, P=0.22). The rate of death from any cause was also reduced with Ticagrelor (4.5%, vs. 5.9% with Clopidogrel; P<0.001) (12)

We currently use Ticagrelor in patients admitted with STEMI prior to PPCI. Recently published data suggests however that even with this rapidly effective oral agent, it is not fully functional at the time of PPCI given the short timelines involved (13, 14)

Ticagrelor differs from the thienopyridine class of antiplatelet agents (Clopidogrel, Prasugrel, and Ticlopidine) as it does not exist as a prodrug and thus does not require biotransformation by hepatic enzymes before becoming active. Also Ticagrelor binds reversibly to P2Y₁₂ receptors leading to a faster onset and offset than Clopidogrel (15). Moreover, in the RESPOND study, Ticagrelor therapy was associated with uniform and superior platelet inhibition in both previously identified Clopidogrel responders and non-responders, and that inhibition, in turn, was associated with an extremely low prevalence of high on-treatment platelet reactivity (16).

Ticagrelor has recently received recommendation in the ESC guideline as a front-line treatment option for STEMI and NSTEMI (17, 18)

Ideally a full antiplatelet effect would be evident at the start of the PPCI, whereas in practice dosing of Clopidogrel, Prasugrel or Ticagrelor typically occurs on admission to hospital (possible only 10-20 minutes prior to PPCI).

Cangrelor is an adenosine diphosphate analogue that reversibly binds to and inhibits the P2Y12 ADP receptor. It has a half-life of 3 to 6 minutes and, when given as a bolus plus infusion, quickly and consistently inhibits platelets to a high degree, with normalisation of platelet function within 60 minutes after discontinuation (19).

Cangrelor [Kengrexal (EU), Kengreal (USA)] has been licensed for use in Europe, USA and the UK since March 2015, June 2015 and July 2015 respectively. Co-administered with Aspirin, is indicated for the reduction of thrombotic cardiovascular events in adult patients with coronary artery disease undergoing percutaneous coronary intervention (PCI) who have not received an oral P2Y12 inhibitor prior to the PCI procedure and in whom oral therapy with P2Y12 inhibitors is not feasible or desirable.

The use of Cangrelor in patients undergoing PCI has been studied in three phase 3 trials, the Cangrelor versus Standard Therapy to Achieve Optimal Management of Platelet Inhibition (CHAMPION) PCI study, the CHAMPION PLATFORM study and the CHAMPION PHOENIX study (19)(20)(21). In the CHAMPION PCI and the CHAMPION PLATFORM studies, Cangrelor, compared to oral Clopidogrel was not associated with a significant reduction in the primary efficacy end point (All cause death, MI or ischaemia driven revascularization at 48 hours) but was associated with reductions in secondary end points, including the rate of stent thrombosis, with no excess in severe bleeding. In the CHAMPION PLATFORM study there was also a reduction of the pre-specified secondary endpoint of death in the Cangrelor arm. The CHAMPION PHOENIX trial enrolled 11,145 patients undergoing PCI for SA, NSTEMI/UA or STEMI. Patients were randomized to either IV Cangrelor followed by Clopidogrel or oral Clopidogrel (300 or 600 mg) before during or immediately after PCI. In this study patients treated with the intravenous agent were significantly less likely to experience one of the primary endpoints (all cause death, MI or ischaemia driven revascularization at 48 hours), with no significant increase in bleeding. The study included 1992 patients with STEMI, who appeared to have a similar benefit to the SA and NSTEMI patients. Currently there are no data comparing the relative efficacy of Cangrelor with the more potent and rapidly acting Ticagrelor in patients undergoing PPCI for acute STEMI of less than 12 hours duration.

2.2 RATIONALE FOR CURRENT STUDY

Gastrointestinal absorption during a STEMI is not equivalent to that of a resting patient (22). Hypotension and/or diversion of splanchnic blood flow are likely to slow drug absorption and the intrinsic increase in platelet activity seen during STEMI (23) (24) may also inhibit the antiplatelet effect of drugs. A previous pharmacokinetic study has shown reduced drug absorption during STEMI (25). Administration of Morphine to ease STEMI pain appears to attenuate the antiplatelet effects of newer P2Y12 inhibitors in the hours after primary PCI (26).

In the current study we aim to demonstrate whether intravenous Cangrelor has a better antiplatelet effect than Ticagrelor during the primary angioplasty (STEMI patients), and investigate the pharmacodynamics properties of these agents in the setting of STEMI by assessing the impact of these agents on a variety of STEMI related outcome variables.

A number of methods have been developed to assess the effect of $P2Y_{12}$ receptor inhibition. Their effect is probably best measured using techniques that specifically measure $P2Y_{12}$ ADP receptor activation, such as vasodilator stimulated phosphoprotein phosphorylation (VASP) utilising flow cytometry, and the VerifyNow $P2Y_{12}$ near patient system (Accumetrics, San Diego, CA).

We will utilise both of these methods in this study.

3. STUDY OBJECTIVES

- 1) To determine the degree and time-course of platelet inhibition in patients admitted with STEMI treated with IV Cangrelor vs oral Ticagrelor.
- 2) To assess the impact of Cangrelor vs Ticagrelor on the index of myocardial microcirculatory resistance using IMR.
- 3) To investigate the impact of Cangrelor vs Ticagrelor on markers of PPCI success (TIMI flow grade assessment to evaluate coronary blood flow after PPCI).
- 4) To assess ST segment resolution post PPCI.
- 5) To investigate the impact of Cangrelor vs Ticagrelor on initial myocardial infarct size based on Peak Troponin.
- 6) To investigate the impact of Cangrelor vs Ticagrelor on final myocardial infarct size by CMR at three months post PPCI.

4. STUDY DESIGN

This is an open label randomised controlled pilot trial. We will enrol 100 patients (50 in each arm). We anticipate the conclusion of subject recruitment in 12 months from the study start date, with a further 6 months for data analysis and manuscript preparation. Patients in the intravenous Cangrelor arm will receive Cangrelor as an initial bolus dose given as per body weight followed by an intravenous infusion for no longer than three hours (The total dose of IV Kengrexal to be administered based on average body weight of 80 Kg is 510 micrograms/kg given over two hours), they will then switch to oral Ticagrelor given at maintenance dose of 90mg twice daily for 12 months. Patients in the oral Ticagrelor arm will receive Ticagrelor at a loading dose of 180mg followed by maintenance dose of 90mg twice daily for 12 months. All the 100 participants will undergo a CMR scan three months post PPCI.

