5.3 RANDOMISATION

Potential patients will be reviewed by a member of the research team before randomisation to confirm eligibility. Once the eligibility of the patient is confirmed by the trial coordinators and the verbal assent is gained, randomisation will be carried out prior to patient's transfer to the cardiac catheter suite. Randomisation will be performed via a secure online web-based service. There will be a single password which will give access for randomisation for the trial on fully encrypted password-protected computers at the heart and lung centre, New Cross Hospital. The system is accessed via a secure connection (SSL) over the internet. This connection encrypts data between the user's internet browser and the server. Online randomisation is achieved by the trial coordinator entering a patient identifier (text field will be unique), own email address and the randomisation system password. Randomisation is by random permuted blocks to oral Ticagrelor or IV Cangrelor in 1:1 ratio. An email notification is generated displaying the chosen treatment group or code and sent to the email address given by the user randomising and the administrator email address. The administrator email address is the one provided when the system is set up (usually a trial coordinator or central trial email address). There is only one password and only members of the research team can perform a randomisation.

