6.4 TIMI Flow Grade

In acute ST elevation myocardial infarction early reperfusion of the occluded coronary artery, limits the size of infarction, reduces the degree of left ventricular dysfunction, and improves survival (32). Assessment of the degree of reperfusion was achieved using the Thrombolysis in Myocardial Infarction (TIMI) flow grading system developed in the TIMI 1 trial (Grade 0—No perfusion; Grade 1—Penetration without perfusion; Grade 2—Partial perfusion; Grade 3—Complete perfusion) (33). A larger improved survival was observed in patients who achieved TIMI grade 3 flow (34, 35). There is a nearly linear correlation between higher rates of early TIMI grade 3 flow and improved survival (35).

In our study, we will assess the index of blood flow through the culprit coronary artery using TIMI Frame Count (TFC). The TFC is a simple, reproducible, objective, and quantitative index of coronary flow that allows standardization of TIMI flow grades and facilitates comparisons of angiographic end points between trials (36).

The number of cine-frames required for contrast to first reach standardized distal coronary landmarks in the infarct-related artery (the TIMI frame count) will be measured with a frame counter on the GE cine-viewer. The first frame to be used for TIMI frame counting will be the first frame in which dye fully enters the artery. The last frame is defined as the frame when dye first enters the distal landmark branch.

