6.7 ST Segment Resolution post-acute Myocardial Infarction

Percutaneous coronary intervention is the preferred treatment strategy in patients with acute ST-Elevation myocardial infarction (STEMI). It promotes an early and sustained restoration of epicardial blood flow in the target vessel (17). (45).

Successful reperfusion of the epicardial vessel is essential, but it is the microvascular flow that most strongly correlates with outcome. ST-segment changes reflect myocardial rather than epicardial flow and hence provide prognostic information beyond that provided by coronary angiogram alone (46-49).

The resolution of the ST-segment after the institution of reperfusion therapy is an important

predictor of patency of the artery related to the event and of effective microcirculatory perfusion (50).

Various studies have shown a remarkably consistent relationship between the degree of ST resolution and subsequent mortality (51). ECG is useful, simple, noninvasive, broadly accessible, easily repeatable/applied, and affordable tool (52).

The persistence of ST-segment elevation on the ECG, despite the restoration of a normal epicardial flow, reflects a poor prognosis and correlates with larger infarct size and higher combined rate of severe cardiovascular adverse events (53). In our study, an ECG will be recorded 90-120 minutes post PPCI to assess the degree of ST segment resolution.

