6.8 CMR Assessment of Myocardial Infarct Size

CMR has become the gold standard for surrogate endpoints in clinical trials. CMR of myocardial infarction has been correlated with histology (54). It can accurately measure infarct size (55), LV volumes (56), myocardial salvage (57), microvascular obstruction (MVO) (58) and myocardial oedema (area at risk). Myocardial infarct size, myocardial salvage and MVO have all been shown to be associated with worse outcomes.

CMR assessment of final infarct size will be performed at three months post STEMI. Infarct size will be quantified by planimetering the region of hyperintensity in the myocardium 10 minutes following gadolinium contrast administration. We will notify patients and their responsible general practitioners about the CMR examination result in writing.

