11. REGULATORY ISSUES

11.1 CONFIDENTIALITY

Blood samples will be anonymised with members of the research team at New Cross Hospital having access to the patient's details. All data collected on the patient will be stored in an anonymised fashion on fully encrypted password-protected computers at New Cross Hospital. The study will be archived for 5 years after the study has ended and then destroyed in line with the Research and Development Department policy.

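### In an open-label trial, the plan states no masking for reading the TIMI frame count, ST-segment resolution or CMR infarct size

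*Combined protocol and SAP*

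**What the plan says.** Section 4: "This is an open label randomised controlled pilot trial" and "We will enrol 100 patients (50 in each arm"). Under Section 5.3 a member of the research team randomises each patient, and "An email notification is generated displaying the chosen treatment group or code and sent to the email address given by the user randomising".

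The arms look different in use. Under Section 6.2.2, ticagrelor is given orally on the ward. Cangrelor is a bolus and infusion started in the catheter lab before PCI and run for at least two hours, or for the length of the procedure if longer. Both arms then take the same maintenance ticagrelor.

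The three outcomes at issue are c, d and f in Section 4.1:

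- **TIMI frame count (6.4).** Frames are counted on the cine-viewer. The first frame is set by when dye has fully entered the artery, and "The last frame is defined as the frame when dye first enters the distal landmark branch".
- **ST resolution (6.7).** The plan says "an ECG will be recorded 90-120 minutes post PPCI to assess the degree of ST segment resolution". It gives no measurement method and no reader.
- **CMR infarct size (6.8).** It is obtained by "planimetering the region of hyperintensity in the myocardium". Section 6.8 also provides for a written result to patient and GP, and Section 10.2 for a clinical report to the care team.

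None of these sections says who reads the files or what that person knows. The nearest text is Section 11.1: "All data collected on the patient will be stored in an anonymised fashion".

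**The concern.** Open-label treatment does not require open-label reading. Where a measurement depends on choosing a frame or drawing a contour, a reader who knows the arm can shift the values in that arm without intending to. Recruiting more patients does not average out such a shift.

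The plan gives readers grounds for an expectation. Sections 1 and 2.2 argue that oral P2Y12 inhibitors are poorly absorbed in STEMI. Objectives 3, 4 and 6 rest on these three readings. Pilot status does not make the point harmless: Section 7.1 says the study will inform power calculations for later studies, and Section 8 says positive results might lead to use of cangrelor in practice. A reading artefact could be carried into either.

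**Working it through.** **1. Is masking stated anywhere?** The available text contains no provision for masked readers, a core laboratory, duplicate reading or adjudication. Blinding is mentioned only for other trials (the account of PLATO in Section 2.1, and reference titles). Section 11.1 concerns how data are stored. It does not mention the treatment arm or the readers, so it does not supply masking.

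**2. Which outcomes depend on a reader?**

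| Outcome (Section 4.1) | How it is obtained | Exposure |
|---|---|---|
| a. Platelet inhibition | VerifyNow and VASP assays (6.3) | low |
| b. IMR | automated calculation (6.6) | low |
| c. TIMI frame count | reader picks frames (6.4) | yes |
| d. ST resolution | method not given (6.7) | cannot be excluded |
| e. Peak troponin | laboratory assay (6.5) | low |
| f. CMR infarct size | planimetry (6.8) | yes |

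**3. Could a reader know the arm?**

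- *Angiogram:* anyone in the catheter lab can see whether an infusion is running. Appendix 2 places TIMI flow at the end of PPCI.
- *ECG at 90-120 minutes:* the infusion may still be running or have recently stopped, depending on the length of the procedure.
- *CMR at three months:* both arms are on the same maintenance drug, so current medication does not reveal the arm. A reader would have to remember it or see it in the chart.

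**4. What could a shift do?** The plan has no figure to reproduce: it gives no alpha, SD or effect size, and Section 7.1 says no formal sample size calculation was done. The following is an illustration. Assumptions: no true effect, a continuous outcome, a normal approximation, a two-sided 5% level, and reading that moves one arm by b standard deviations.

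False-positive rate = P(Z > 1.96 − b/√(2/n)) + P(Z < −1.96 − b/√(2/n)), with n per arm.

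For n = 50 (Section 4), √(2/50) = 0.2, so b = 0.2 gives b/0.2 = 1.0 and a rate of P(Z > 0.96) + P(Z < −2.96) = 0.1685 + 0.0015 ≈ 0.170. The value n = 40 is assumed, to allow for withdrawals (Section 5.6) and missed or contraindicated scans (Section 5.1).

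| Assumed shift b (SD) | n = 50 per arm | n = 40 per arm |
|---|---|---|
| 0 | 5.0% | 5.0% |
| 0.1 | 7.9% | 7.3% |
| 0.2 | 17.0% | 14.6% |
| 0.3 | 32.3% | 26.9% |

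For the same shift, the rate is higher with the larger n. For scale, the smallest observed difference that reaches significance with 50 per arm is 1.96 × 0.2 = 0.39 SD. A shift of 0.2 SD is about half of that.

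**The case against.** The strongest reply is that silence is not a prescription. The plan never says that the treating team reads the files, and readers may be masked in practice. A reader might infer that following the plan must produce unmasked readings. The documents do not support that; they show only that masking is not stated and nothing secures it. A reader might also assume that all three outcomes are read by hand. That is supported for frame counts and planimetry, but only inferred for the ECG.

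The numerical illustration has limits. The shifts of 0.1 to 0.3 SD have no source in the documents. Section 7 states no alpha, allows non-parametric tests, and uses Fisher's exact test for dichotomous variables. If ST resolution is analysed as a category, the table does not apply to it.

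The CMR is also less exposed than the angiogram, because treatment at three months is the same in both arms. The first-listed objective and outcome, platelet inhibition, is assay-based.

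Finally, stripping a file of labels may not stop an operator from recognising a case, and a reader who has already written the clinical CMR report is no longer naive.

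All of this stands, and it narrows the point without removing it. Section 6.4 describes the frame count as objective, but someone still has to choose the frames. The last objection bears on how masking is done, and the remedy takes it into account.

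**Conclusion.** The concern holds for outcomes c, d and f. The trial is open label, at least two of these outcomes require judgement, and the plan contains nothing to keep readers from knowing the arm. The exposure is clearest for the angiogram and the early ECG.

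The size and direction of any shift are unknown. It is tempting to conclude that the plan will manufacture a cangrelor benefit. The documents give reasons why a reader might expect one, but no evidence that readings would move that way or by how much. The rates of 7.9% to 32.3% (50 per arm) and 7.3% to 26.9% (an assumed 40 per arm) show what shifts of 0.1 to 0.3 SD would do under the stated assumptions. They are not estimates for this trial.

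The point does not extend to the trial's results as a whole: platelet inhibition, troponin and IMR are much less exposed. It should be settled before any research reading begins.

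**What to change.** Add to Sections 6.4, 6.7 and 6.8:

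- Cine, ECG and CMR files are given a code and stripped of arm, drug and chart data.
- They are read in random order by an existing team member who, where possible, did not treat or randomise that patient.
- Values are locked before the allocation is linked.
- For CMR, the research contour is drawn before the clinical report is prepared with chart access. The letter to patient and GP stays separate.

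Section 6.7 should also state how ST resolution is measured. If masked reading is already the practice, a sentence in each section is enough.

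The number of patients, visits and treatments does not change. In the illustration, removing the shift (b = 0) returns the false-positive rate to 5.0%. The cost is some file-coding work and slightly later research values, which fits within the six months that Section 4 already sets aside for analysis and manuscript preparation. The documents do not describe staffing, so whether a non-treating reader is available for every file must be confirmed locally. Where none is, the coded, shuffled and locked reading still gives partial protection, and the report should say which files were read that way.

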6.2 Sampling and Dosing

6.2.1 Study subjects will have a $P2Y_{12}$ inhibitor administered (Ticagrelor or Cangrelor) after recorded verbal assent following randomisation. The time of loading dose will be recorded and the patient transferred to the cardiac catheterization suite. After the insertion of the radial or femoral sheath, 10 ml of whole blood will be drawn from this sheath at the first intracoronary balloon inflation time. A further 10 ml will be taken 4 hours post dosing (or as close as is practicable). Further sampling (15 ml) on the ward will take place 24-36 hours post dosing from an anticubital vein using a 21-gauge needle (see study summary tables). Samples taken will be analysed to assess $P2Y_{12}$ activity using VerifyNow TM (Accumetrics, San Diego, California, USA) and VASP Flow Cytometry tests. Peak Troponin levels will be assessed as well using the same blood samples.

6.2.2 Dosing: Patients will be divided into two arms; Oral Ticagrelor (50 patients) and Intravenous Cangrelor (50 patients) arms.

Ticagrelor arm: Patients will receive Ticagrelor 180mg loading dose on the cardiology ward prior to transfer to the catheter lab. Thereafter, a maintenance dose of 90mg twice daily will be given and continued for 12 months duration.

Cangrelor arm: Patients will receive Cangrelor administered at a rate of 30 micrograms/kg intravenous bolus followed immediately by 4 micrograms/kg/min intravenous infusion. The bolus and infusion will be initiated in the cardiac catheter lab prior to the PCI procedure and continued for at least two hours or for the duration of the procedure (to increase up to three hours), whichever is longer. 30 minutes prior to stopping Cangrelor infusion, Ticagrelor 180 mg will be given followed by 90mg twice daily maintenance dose continued for duration of 12 months. Cangrelor will be obtained directly from The Medicines Company, retained at the

pharmacy department at New Cross Hospital and issued by the pharmacy department for our clinical trial purposes only. Ticagrelor will be received by the pharmacy department and designated for our clinical trial purposes only.

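### Section 4 moves cangrelor patients onto ticagrelor at 90 mg with no load, while section 6.2.2 gives them 180 mg half an hour before the infusion ends

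*Combined protocol and SAP*

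**What the plan says.** Section 4 (Study Design) describes the cangrelor arm as receiving a bolus and an infusion of up to three hours, after which "they will then switch to oral Ticagrelor given at maintenance dose of 90mg twice daily for 12 months". No loading dose is mentioned for this arm. The next sentence does give one for the comparator: "Patients in the oral Ticagrelor arm will receive Ticagrelor at a loading dose of 180mg followed by maintenance dose of 90mg twice daily".

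Section 6.2.2 (Dosing) describes the same step for the same patients differently: "30 minutes prior to stopping Cangrelor infusion, Ticagrelor 180 mg will be given followed by 90mg twice daily maintenance dose". The infusion itself is to be "continued for at least two hours or for the duration of the procedure (to increase up to three hours), whichever is longer".

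The Appendix 2 tables list the start of ticagrelor or cangrelor but say nothing about the transition dose. No other part of the protocol states which section prevails.

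**The concern.** At one step, for one arm, the first oral dose is 90 mg in one section and 180 mg in the other. Section 4 also appears to place that dose after the infusion, where section 6.2.2 places it before the infusion ends.

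The step matters pharmacologically on the protocol's own account. Section 2.1 says cangrelor wears off quickly, "with normalisation of platelet function within 60 minutes after discontinuation". Section 2.2 says of STEMI patients that "Hypotension and/or diversion of splanchnic blood flow are likely to slow drug absorption". A smaller and later oral dose could therefore weaken platelet inhibition in the hours after PPCI.

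It could also alter the 4-hour VerifyNow and VASP readings, which are a listed outcome (section 4.1, item a) and part of the time-course named in objective 1 (section 3). The balloon-time sample comes before the transition and is unaffected. An effect at 24-36 hours is not shown.

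**Working it through.** **1. Is section 4 merely loose about doses in general?** It gives the cangrelor total as "510 micrograms/kg given over two hours". Section 6.2.2 specifies "Cangrelor administered at a rate of 30 micrograms/kg intravenous bolus followed immediately by 4 micrograms/kg/min intravenous infusion". Over 120 minutes:

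30 + 4 × 120 = 510 micrograms/kg.

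The two sections agree exactly on cangrelor, so the discrepancy is confined to the ticagrelor transition.

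**2. The transition, side by side.**

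| | Section 4 | Section 6.2.2 |
|---|---|---|
| First ticagrelor dose, cangrelor arm | 90 mg | 180 mg |
| Timing | after the infusion, if 'then' is strict | 0.5 h before the infusion stops |
| Later dosing | 90 mg twice daily, 12 months | 90 mg twice daily, 12 months |

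The ratio of first doses is 90/180 = 0.5. On a twice-daily schedule no second 90 mg dose falls before the 4-hour sample, so the total oral dose by then is 90 mg against 180 mg.

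**3. Timing relative to the 4-hour sample.** Assume that the 4 hours run from the start of cangrelor. Let S be the time the infusion stops; section 6.2.2 gives S = 2 to 3 h.

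- Section 6.2.2: dose at S − 0.5 = 1.5 to 2.5 h, which is 2.5 to 1.5 h before the sample.
- Section 4, strict reading: dose at S or later, so no more than 4 − S = 2.0 to 1.0 h before the sample.
- Minimum delay: S − (S − 0.5) = 0.5 h.
- Platelet function back to normal after cangrelor, by the section 2.1 figure: no later than S + 1 = 3 to 4 h.

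On this clock, cangrelor's effect should have gone by the 4-hour sample, and the reading in this arm then depends largely on the oral dose.

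**4. What cannot be computed.** The only onset figure is in the lay summary (section 1), and it refers to healthy stable patients. The protocol has no data comparing 90 mg with 180 mg on either platelet assay. Neither a gap in cover nor a shift in the 4-hour reading can be estimated.

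**The case against.** The strongest reply is that section 4 is a design overview from which nobody could dose a patient. It gives neither the bolus dose nor the infusion rate. Anyone giving cangrelor must use section 6.2.2, where the 180 mg instruction sits in the same paragraph. Section 6.2.2 also limits drug access to the research team, and section 11.7 provides training in giving cangrelor. Section 4 omits a load without forbidding one, and could be read as giving only the long-term regimen.

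Much of this stands. Misdosing is unlikely and the number affected is probably small. The timing conflict depends on a strict reading of 'then' and on the assumed time origin, and section 6.2.1 allows some latitude in when the 4-hour sample is drawn. The factor of 0.5 is a dose ratio and says nothing about effect size.

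The incomplete-summary reading is less persuasive. Section 4 distinguishes load from maintenance, states the load for one arm, and names only the maintenance dose as what the other arm switches to. The natural reading is that cangrelor patients get no load. That is a dosing statement in the design section of a drug trial, and it conflicts with the operative text.

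**Conclusion.** The contradiction is real and section 4 is wrong as written, on the judgement that the fuller dosing text in section 6.2.2 is what was intended. The dose conflict (90 mg against 180 mg) is clear. The timing conflict of at least 0.5 h is softer, and the intervals before the 4-hour sample also assume that sample is timed from the start of cangrelor.

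The rule applies to all 50 cangrelor patients. The practical consequence is limited to anyone who relies on the design section, and reaches early cover after PPCI and the 4-hour platelet readings. Neither the number of patients affected nor the size of the effect can be estimated from the documents. It should be corrected, but it does not call the design into question.

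**What to change.** Amend section 4 so that the cangrelor arm receives ticagrelor 180 mg half an hour before cangrelor is stopped, then 90 mg twice daily for 12 months, in line with section 6.2.2. The investigator should first confirm that this is the intended regimen. The cost is one clause in a protocol amendment; sample size, visits and drug supply do not change.

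A separate, optional addition is to record the clock times of the transition ticagrelor dose and of the end of the infusion. Section 6.2.1 records the time of the load before transfer to the catheter suite, which does not clearly capture either. This adds 50 × 2 = 100 entries and would help in interpreting the 4-hour readings, but the contradiction is resolved without it.
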